7.4.1.8. Additional Adverse Event (AE) Reporting Requirements for Canadian investigators

Health Canada requires pharmaceutical manufacturers to expeditiously report domestic cases of unusual failure in efficacy (UFIE) for new drugs to the Marketed Health Products Directorate (MHPD) within 15 days of first notification. This regulation applies to marketed drugs, and used as directed per the Canadian prescribing information, including those drugs used in Phase IV (non CTA filed) clinical trials.

Adverse event (AE): Any untoward medical occurrence in a patient or clinical investigation subject administered a pharmaceutical product and which does not necessarily have to have a causal relationship with this treatment. An AE can therefore be any unfavourable and unintended sign (including an abnormal laboratory finding) symptom or disease (new or exacerbated) temporally associated with the use of a Medicinal Product. **For a marketed Medicinal Product, this can also include failure to produce expected benefits (i.e. lack of efficacy, with or without an adverse event),**

In order for GSK to comply this Canadian regulatory requirement, Canadian investigators are required to collect, record and report lack of efficacy events as per the table in [Appendix 4](#) Section 12.4.1.

All paper forms are required to be faxed to GSK Canada's Drug Safety department at [PP](#) within 24 hrs of first awareness.

7.4.2. Pregnancy

- Details of all pregnancies in female subjects will be collected after the start of Screening and until the follow-up contact.
- If a pregnancy is reported then the investigator should inform GSK within 2 weeks of learning of the pregnancy and should follow the procedures outlined in [Appendix 7](#).

7.4.3. Medical Device Incidents (Including Malfunctions)

Procedures for documenting medical device incidents are provided in [Appendix 6](#).

7.4.4. Electrocardiogram (ECG)

A Single 12-lead ECG will be obtained at Screening using an ECG machine provided by the investigational site that automatically calculates the heart rate and measures PR, QRS, QT, and QTc intervals.

The 12-lead ECG measurement and rhythm strip (10 seconds) will be obtained before spirometry testing. ECG measurement should be obtained after subjects have rested for approximately 5 minutes then the subjects should be placed in the supine position for the ECG measurements. An ECG is only required at Screening Visit 1 for eligibility assessment only.

The investigator, a designated sub-investigator, or other appropriately trained site personnel will be responsible for performing and interpreting the 12-lead ECG at Screening Visit 1. The investigator must provide his/her dated signature on the original paper tracing, attesting to the authenticity of the ECG machine interpretation.

7.5. Genetics

Information regarding genetic research is included in [Appendix 3](#)

8. DATA MANAGEMENT

- For this study subject data will be entered into GSK defined CRFs, transmitted electronically to GSK or designee and combined with data provided from other sources in a validated data system.
- Management of clinical data will be performed in accordance with applicable GSK standards and data cleaning procedures to ensure the integrity of the data, e.g., removing errors and inconsistencies in the data.
- Adverse events and concomitant medications terms will be coded using MedDRA (Medical Dictionary for Regulatory Activities) and an internal validated medication dictionary, GSKDrug.
- CRFs (including queries and audit trails) will be retained by GSK, and copies will be sent to the investigator to maintain as the investigator copy. Subject initials will not be collected or transmitted to GSK according to GSK policy.

9. STATISTICAL CONSIDERATIONS AND DATA ANALYSES

9.1. Hypotheses

The primary purpose of this study is to demonstrate improvements in lung function for subjects treated with UMEC/VI compared with UMEC for 24 weeks.

The primary endpoint is change from baseline in trough FEV₁ at Week 24.

The null hypothesis is no difference between treatment groups ($H_0: \mu_T - \mu_S = 0$), with the alternative hypothesis that there is a difference between treatment groups ($H_1: \mu_T - \mu_S \neq 0$), where μ_T is the mean change from baseline for UMEC/VI and μ_S is the mean change from baseline for UMEC.

9.2. Sample Size Considerations

The primary endpoint is change from baseline in trough FEV₁ at Week 24. As an important aim of the study is to compare UMEC/VI, UMEC and salmeterol with respect to HRQoL the sample size has been calculated to provide sufficient power for the comparison of the primary and secondary endpoint TDI, at Week 24.

The sample size calculations use a two-sided 5% significance level and an estimate of between subject standard deviation for TDI of 2.94 units. The estimate of SD is based on DB2113373 [Donohue, 2013], a study which consisted of treatment arms of UMEC/VI 62.5/25, UMEC 62.5 VI (Vilanterol) 25mcg and placebo and is the value at Day 168 in a subgroup of subjects who were ICS free at screening. Based on these data, 727 evaluable subjects per treatment arm will be required to provide 90% power to detect a statistically significant difference if the true difference is 0.5 units, ½ the MCID, between UMEC/VI and UMEC. The smallest observed effect predicted to result in a statistically significant difference between treatment groups is 0.31 units.

With this number of evaluable subjects per arm, the study will have >99% power assuming a true treatment difference of 80mL between UMEC/VI and UMEC for trough FEV₁ at 24 weeks at the two-sided 5% significance level. This calculation uses a SD for trough FEV₁ of 240mL, based on prior results for trials comparing dual bronchodilators versus single bronchodilators (Donohue, 2013; Bateman, 2013). The smallest observed effect predicted to result in a statistically significant difference between treatment groups is 25mL.

In order to account for a 10% withdrawal rate, approximately 808 subjects per treatment arm will be randomised.

9.2.1. Sample Size Sensitivity

The assumption of a SD of 2.94 units for the TDI total score is based on estimates from previous studies. The following table presents the power achieved with the proposed sample size of 727 randomised subjects per arm, should the assumption around the SD of the data change.

The actual assumptions used in the sample size calculation are shaded.

Endpoint	Between subject SD	Treatment Difference	Power
TDI	2.54	0.5	96%
	2.74	0.5	94%
	2.94	0.5	90%
	3.14	0.5	86%
	3.34	0.5	81%

9.2.2. Sample Size Re-estimation or Adjustment

No sample size re-estimation is planned for this study.

9.3. Data Analysis Considerations

9.3.1. Analysis Populations

Population	Definition / Criteria	Analyses Evaluated
All Subjects Enrolled (ASE)	
 All subjects for whom a record exists in the study database, including screen failures and any subject who was not screened but experienced an SAE between the date of informed consent and the planned date of the Screening visit. 	
 Subject Disposition Reasons for withdrawal prior to randomisation Inclusion, exclusion and randomisation criteria deviations SAEs for non-randomised subjects
Intent-to-treat (ITT)	
 All randomized subjects, excluding those who were randomized in error and received at least one dose of study medication. A subject who is recorded as a screen or run-in failure and also randomized will be considered to be randomized in error. Any other subject who receives a randomization number will be considered to have been randomized. Displays will be based on the treatment to which the subject was randomized. 	
 Study Population Efficacy Safety
Intent-to-treat ICS free (ITT ICS free)	
 All subjects in the ITT Population who have not received ICS. 	
 Study Population Efficacy Safety

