9.4. Key Elements of Analysis Plan

Treatment Comparisons

The primary treatment comparison of UMEC/VI with UMEC will be performed on the ITT population.

The other treatment comparisons of UMEC/VI and UMEC with Salmeterol will be performed on the ITT population and ITT ICS free population.

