9.4.2. Other Analyses

The MMRM analysis will be repeated for the ITT ICS free population. Estimated differences between UMEC/VI or UMEC and Salmeterol will be presented together with 95% confidence intervals (CIs) for the difference and p-values.

Secondary and other efficacy endpoints and treatment comparisons will be adjusted for multiplicity as per Section [9.4.1](#).

Full details of the analyses to be performed on the other efficacy endpoints will be given in the RAP.

Safety Analyses

Adverse events (AEs) will be coded using the standard GSK dictionary, Medical

Dictionary for Regulatory Activities (MedDRA), and grouped by body system. The number and percentage of subjects experiencing at least one AE of any type, AEs within each body system and AEs within each preferred term will be presented for each treatment group. Separate summaries will be provided for all AEs, drug related AEs, fatal AEs, non-fatal SAEs, AESIs and AEs leading to withdrawal.

Deaths and SAEs will be documented in case narrative format.

Full details of the analyses to be performed on all safety endpoints will be given in the RAP.

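### The ITT sentence is mis-worded, and on either reading a dosed subject randomised in error has no place in the safety summaries by treatment group

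*Protocol*

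**What the plan says.** The table in Protocol Section 9.3.1 defines three populations.

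- **ITT** is "All randomized subjects, excluding those who were randomized in error and received at least one dose of study medication". It then explains the error category: "A subject who is recorded as a screen or run-in failure and also randomized will be considered to be randomized in error". It goes on: "Any other subject who receives a randomization number will be considered to have been randomized". For presentation, "Displays will be based on the treatment to which the subject was randomized". The uses listed for ITT are study population, efficacy and safety.
- **ITT ICS free** is "All subjects in the ITT Population who have not received ICS". It lists the same three uses.
- **All Subjects Enrolled (ASE)** takes in everyone with a database record. Its uses are disposition, reasons for withdrawal before randomisation, deviations from the entry and randomisation criteria, and "SAEs for non-randomised subjects".

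Section 9.4 states that "The primary treatment comparison of UMEC/VI with UMEC will be performed on the ITT population". Section 7.4 names adverse event incidence as the safety endpoint. Section 9.4.2 summarises adverse events by treatment group ("AEs within each preferred term will be presented for each treatment group") and names no other safety set. It also asks for case narratives for deaths and serious adverse events. The ITT sentence is the same in the Amendment 02 text that is bound into the document.

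**The concern.** A population definition should let two programmers build the same analysis set. This one does not, because the dosing clause can attach either to the exclusion or to the inclusion. The ambiguity reaches the primary comparison as well as safety, since both use ITT.

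The more important matter is exposure. Safety summaries should account for everyone who took study drug. Here the rule that protects the efficacy set from record errors also serves as the safety rule, and it removes a group of exposed subjects. Section 7.4.1.1 collects adverse events from the start of study treatment, so these subjects' events would be collected and then have no treatment-group table to go into. A further consequence of using one set for both purposes is that safety follows the randomised arm: events in a subject who took another arm's inhaler would count against a drug that was not taken.

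**Working it through.** The plan states no figure on this point, so the check is logical. Each randomised subject falls into one of four cells, by whether they were randomised in error and whether they took a dose.

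- Literal reading: in ITT if randomised and NOT (in error AND dosed). One relative clause governs both verbs, so both conditions must hold for exclusion.
- Probably intended reading: in ITT if randomised AND NOT in error AND dosed.

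| Randomised in error | Dosed | Literal reading | Intended reading |
|---|---|---|---|
| No | No | In | Out |
| No | Yes | In | In |
| Yes | No | In | Out |
| Yes | Yes | Out | Out |

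The readings disagree in two of the four cells, and both hold never-dosed subjects. The last row is out under either, so the loss of a dosed subject does not depend on how the sentence is parsed.

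The next step is to ask whether another population picks up that last row.

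1. ITT ICS free is a subset of ITT ("All subjects in the ITT Population who have not received ICS"), so it cannot recover anyone whom ITT drops.
2. ASE contains the subject, but its only safety use is "SAEs for non-randomised subjects". The word *other* in "Any other subject who receives a randomization number will be considered to have been randomized" suggests that someone randomised in error is not counted as randomised. On that view the subject's serious events could be shown under ASE, labelled as arising in a non-randomised subject. Non-serious events are not covered.
3. The narratives in Section 9.4.2 carry no population limit, so deaths and serious events would be described there. A narrative is not a treatment-group summary.

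The last step is the size of the category. Section 5.4 defines a run-in failure as a subject who enters run-in and is not randomised, and a screening failure as one who does not enter run-in. By those definitions nobody can be both a failure and randomised. The category in Section 9.3.1 therefore exists only where the record contradicts itself, which points to few subjects. An ordinary ineligible subject who was randomised and dosed, with no failure recorded, stays in ITT.

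**The case against.** The strongest reply is that this is a drafting slip about a rare event. The literal reading serves no purpose, because it would remove erroneously randomised subjects only if they took drug. A comma after the error clause restores the sense. That is a fair account of the intention. It settles the undosed cells but leaves the dosed-in-error cell where it was.

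Four stronger conclusions are tempting, and the documents do not support them.

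- A reader might infer that ITT certainly keeps undosed subjects and so dilutes the adverse event percentages. That holds only on the literal reading.
- A reader might infer that serious events in these subjects are lost altogether. Section 7.4.1.1 requires all serious adverse events to be recorded and reported to the sponsor within 24 hours, Section 9.4.2 provides narratives, and ASE may list them. What is missing is a display by treatment arm.
- A reader might take the exclusion to cover every subject who breached an entry criterion. It covers only those recorded as screen or run-in failures, and criteria deviations are already reported on ASE.
- A reader might put a number on the problem, or suppose that the failure status could be entered after dosing to remove a subject. The protocol gives no rate and says nothing about when that entry is made relative to dosing. Any percentage applied to the 2424 planned subjects would be a guess.

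It could also be said that the analysis plan can settle this. The protocol, however, fixes the definition itself. An analysis plan that follows it inherits the gap, and one that departs from it contradicts the protocol.

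**Conclusion.** The point holds in a limited form. The ITT sentence is ambiguous about undosed subjects. Independently of that ambiguity, it places dosed subjects recorded as randomised in error outside the only set used for safety by treatment group. Their non-serious adverse events have no assigned summary, and their serious events have no treatment-arm display. Safety is also shown by randomised arm, with no rule for treatment received.

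The number affected is not stated and is probably small. The effect on the efficacy estimates is likely to be slight, and the sample-size figures in Section 9.2 do not depend on it. The conclusion rests on the population table in Section 9.3.1 as written and on Section 9.4.2 naming no further safety set. It does not rest on any assumed error rate. The correction is worth making because it is cheap and because accounting for every exposed subject should not turn on an administrative status.

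**What to change.** Make two wording changes in Section 9.3.1.

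1. Rewrite the ITT sentence so that the dosing clause can be read only one way. If a dose is meant as an entry condition, say that ITT comprises randomised subjects who took at least one dose of study medication, leaving out those recorded as randomised in error, grouped by randomised arm. If a dose is not meant as a condition, remove the clause.
2. Add a Safety population: all subjects who took at least one dose of study treatment, including any recorded as randomised in error, grouped by treatment actually received. Take safety off the list of uses for ITT, and name the new population in the safety paragraph of Section 9.4.2. If ICS-free safety tables are still wanted, derive them from the Safety population.

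The cost is text in the protocol and the matching text in the analysis plan. No new visits, assessments or subjects are needed, and Section 6.8 already requires records of the inhalers dispensed and doses taken. The changes should be made before unblinding, so that the choice of population cannot appear to follow the data.

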6.3. Treatment Assignment

Subjects who meet the randomization criteria will be assigned to one of the 3 study treatments in accordance with the randomization schedule generated by Clinical Statistics, prior to the start of the study, using validated internal software.

Once a randomization number is assigned to a subject, it cannot be reassigned to any other subject in the study.

This study will utilize RAMOS NG, which will provide a means for central allocation of drug. Each investigator will be supplied with sufficient supplies to conduct the trial. Additional treatment packs will be supplied as needed to the sites. Details of how to use the RAMOS NG to randomize subjects is provided in the SRM.

The duration of treatment for each subject is 24 weeks. On the morning of each clinic study visit, subjects will refrain from taking their morning dose of study treatment until instructed to do so by clinic personnel. On the other days during the treatment period (i.e. “non-clinic days”), subjects will be instructed to self-administer their study treatment in the morning and evening. Subjects should enter the time they take their study treatment in the eDiary.

Subjects will be randomly assigned to one of the blinded study treatment regimens in equal proportion (ratio of 1:1:1):

- UMEC/VI 62.5/25 mcg once daily via ELLIPTA + placebo twice daily via DISKUS
- UMEC 62.5 mcg once daily via ELLIPTA + placebo twice daily via DISKUS
- Salmeterol 50 mcg twice daily via DISKUS + placebo once daily via ELLIPTA

The randomisation will be stratified based on **long-acting bronchodilator** usage during the run-in (none or one **long-acting bronchodilator** per day).

Study treatment/investigational product will be dispensed at Visits 2, 3 and 4.

In order to ensure subjects have sufficient doses of study treatment, they must return to clinic within 30 days from V2 and 60 days from V3 respectively (see Time and event table Section [7.1](#)).

Used study drug and rescue medication will be collected at Visits 3, 4 and 5 or at the Early Withdrawal Visit.

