6.7.1. Study Treatment Return

All used and unused ELLIPTA and DISKUS inhalers and albuterol/salbutamol will be returned to GSK at the end of the study to be available for disposal. In some instances for sites outside the US, study supplies will be disposed of locally either by the site, the country medical department or third-party vendor. Detailed instructions for the return of the study drug can be found in the SRM.

Study treatment will be collected at Visit 3, 4 and 5 or at the Early Withdrawal Visit, if applicable.

For any ELLIPTA or DISKUS inhaler that fails to function properly, the subject should return to the clinic as soon as possible to obtain a new inhaler. The site will contact the RAMOS NG to obtain a new treatment pack number for the subject and dispense a new study treatment kit from the site's investigational product supply as instructed by the RAMOS NG

In addition, any ELLIPTA that fails to function properly must be identified and returned to GSK for testing.

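### Safety displays are fixed by randomised treatment, so an adverse event that starts on another arm's kit is tabulated under a regimen the subject was not then taking (minor)

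*Protocol*

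**What the plan says.** Protocol section 9.3.1 defines three populations: all subjects enrolled, ITT, and ITT ICS free. The ITT set is "All randomized subjects, excluding those who were randomized in error and received at least one dose of study medication". Its row names study population, efficacy and safety as the analyses it serves, and it carries the rule "Displays will be based on the treatment to which the subject was randomized". The ICS-free set is "All subjects in the ITT Population who have not received ICS"; it also serves safety and has no rule of its own on treatment received. There is no separate safety population.

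Section 9.4.2 describes the safety output. Counts and percentages of subjects with any event, and with "AEs within each preferred term will be presented for each treatment group". It adds: "Separate summaries will be provided for all AEs, drug related AEs, fatal AEs, non-fatal SAEs, AESIs and AEs leading to withdrawal". It makes no exception to the rule in 9.3.1. It also says that deaths and serious events will be written up as narratives, and that "Full details of the analyses to be performed on all safety endpoints will be given in the RAP".

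On supply, section 6.3 says "Study treatment/investigational product will be dispensed at Visits 2, 3 and 4", with central allocation through RAMOS NG. For a faulty inhaler, section 6.7.1 says "The site will contact the RAMOS NG to obtain a new treatment pack number for the subject and dispense a new study treatment kit".

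**The concern.** Analysing by randomised arm protects the efficacy comparison because it preserves the groups that randomisation formed. Safety asks a different question. The safety objective in section 3 concerns the safety and tolerability of three named regimens, so an event should be counted under the regimen the subject was exposed to when it began.

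Under the rule in 9.3.1, a subject randomised to one arm and handed a kit from another has any event on that kit counted in the randomised column. If such errors run in both directions, the columns become more alike and differences shrink towards zero, which is the direction that hides a harm. For rare events, such as fatal, serious or drug-related ones, one misplaced case can change how a table reads.

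This is about which column a dosed subject is counted in. Who belongs to the set is a separate matter.

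**Working it through.** **Is the rule fixed, or left open?** Set 9.3.1 beside 9.4.2. The first names safety as a use of the ITT set and assigns its displays to randomised treatment. The second presents events by treatment group and says nothing on treatment received. Section 9.4.2 sends the detail of the safety analyses to the reporting and analysis plan, but the column rule is already stated in the protocol. A reporting plan that used treatment received for the main safety tables would depart from the protocol's text.

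**Numbers of subjects and dispensings.** Section 9.2 gives 727 evaluable per arm and 10% withdrawal: 727 / (1 - 0.10) = 807.8, so 808 per arm, and 3 x 808 = 2424, as the protocol states. With three scheduled dispensings each, 2424 x 3 = 7272. This is a ceiling for scheduled supply, because subjects who withdraw miss later visits; replacement kits come on top.

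**How many wrong kits (assumed).** The protocol gives no misdispensing rate. Take 0.1% to 0.5% per dispensing as an illustration:
- 7272 x 0.001 = 7 and 7272 x 0.005 = 36 wrong kits.
- If a wrong kit is equally likely to belong to any of the three arms, two thirds hold another arm's treatment: 7.3 x 2/3 = 5 to 36.4 x 2/3 = 24.
- 24 / 2424 is about 1% of subjects, if each error falls on a different subject.

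**Effect on common events (assumed event rates).** Let a share m of each of two arms take the other's treatment throughout. The displayed difference is then (1 - 2m) times the true one.
- m = 1%, true 10% v 6%: (0.10 x 0.99 + 0.06 x 0.01) - (0.06 x 0.99 + 0.10 x 0.01) = 0.0996 - 0.0604 = 0.0392, against 0.0400.
- m = 0.1% to 2% (about 1 to 16 of 808), true 10% v 5%: 5.0 points shows as 4.99 to 4.80.

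Both overstate the effect, since one wrong kit covers only part of the 24 weeks.

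**Effect on rare events.** Suppose two serious events occur on treatment A and none on B, and one of the two subjects had been randomised to B but was on A's kit. By treatment received the count is 2 v 0; by randomised arm it is 1 v 1.

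**What a column rule can correct.** Visits at Weeks 0, 4, 12 and 24 give supply intervals of 28, 56 and 84 days out of 168. A wrong supply from Visit 2 covers 28/168 = 17% of treatment, from Visit 3 56/168 = 33%, and from Visit 4 84/168 = 50%. Placing a subject under the treatment taken for most days would leave the first two in the randomised column, just as now, and would produce a tie in the third. For a single wrong kit, only a flag on the event itself identifies the misattribution.

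**The case against.** The strongest reply is that the point depends on a rare error that the protocol does not describe. Packs are allocated centrally, every rate above is assumed, and the resulting dilution is trivial. This stands, and it is why the point is minor.

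Deaths and serious events will also have narratives, and section 12.4.5 requires a causality assessment for each event. That stands too: individual serious cases are not judged by a column count alone. The summary tables would still show them in the wrong column, and non-serious drug-related events have no such narrative provision.

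Two stronger readings are tempting, and the protocol does not support either:
- A reader might infer that the event is charged to a drug the subject never took. That is true of only some mix-ups. UMEC/VI and UMEC share a component, every arm uses both devices, and treatment is supplied at three visits. A UMEC subject given a UMEC/VI kit still inhaled UMEC, and a subject with one wrong kit was usually on the randomised regimen the rest of the time.
- A reader might infer that no as-treated display will exist at all. The reporting plan is not at hand, and 9.3.1 does not forbid a supplementary listing. One can say only that the protocol states none and fixes the main displays the other way.

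Finally, the records needed may not be to hand. Section 6.8 asks for counts of inhalers dispensed and doses inhaled, and section 6.7.1 mentions a pack number only for replacements. That is a fair caution and is carried into the fix.

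**Conclusion.** The concern holds as a minor point. Section 9.3.1 fixes safety displays to randomised treatment, 9.4.2 makes no exception, and for an objective about the safety of each regimen that is the less suitable choice. After a misdispensing, an event is tabulated under a regimen the subject was not taking when it began.

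On the assumed rates, the effect on common event rates is negligible, about 0.01 to 0.2 of a point on differences of 4 to 5 points. These figures rest on assumed wrong-kit and event rates, on errors mixing evenly between arms, and on full-period exposure to the wrong treatment, so they do not show that the trial's safety comparisons would be materially biased. What remains is the possible misplacement of individual rare or serious events in the summary tables, partly offset by the narratives. The primary analysis and the sample size are untouched.

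**What to change.** In section 9.3.1, limit the as-randomised rule to study population and efficacy displays, and state that safety displays use treatment actually received, as follows:
- A subject who took only a treatment other than the randomised one is shown under the treatment taken.
- A subject who took the randomised treatment for part of the period stays in the randomised column.
- Any adverse event that starts while the subject is on another arm's kit is listed and flagged with the treatment taken at onset.

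The third item does most of the work, since one wrong kit will rarely move a subject between columns.

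The cost is a short addition to the text, one derived variable and one listing. Before relying on it, the sponsor should confirm that the pack numbers dispensed at every visit, and not only replacements, can be obtained from RAMOS NG. The downside is that safety and efficacy column totals may differ by a few subjects, which a footnote can explain. The rule should be set before unblinding, since choosing columns afterwards would lack credibility.
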